8.1.6 Morphine Administration and Analgesic Use

The dose and frequency of morphine administration and analgesic use will be assessed at each on-site study visit based on the patient's concomitant medication use assessment.

8.1.7 Skeletal-related Events and Symptomatic Skeletal Events Assessment

Skeletal-related events and SSEs will be evaluated based on the patient's clinical history and examinations, including but not limited to incidence of fractures and pain. Assessments will be performed at each on-site study visit.

8.1.8 **Progression-free Survival**

Progression-free survival is defined as the duration of time from first dose administration to date of disease progression is objectively documented, including tumor progression, early discontinuation or death prior to data cut-off. Patients alive and progression-free at the time of data cut-off will be censored at the date last known alive. Progression-free survival will be assessed every 8 weeks (\pm 7 days) from the first dose administration up to Week 26, and every 12 weeks (\pm 7 days) thereafter until disease progression according to RECIST v1.1 criteria.

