There will be a Screening period of up to 27 days (Days -28 to -2). Each patient will attend the study center on Day -1 of Cycle 1 for eligibility assessments and on all PK days (Cycle 1: Days 1, 2, 6, 14 and 15; Cycles 2 and 3: Days 1 and 8). Patients in Part 1 may require an overnight stay on Day 1 of Cycle 1. On Days 1, 2, 6 and 14 of Cycle 1 and Day 1 of Cycles 2 and 3, the NOX66 morning administration will occur at the study center under medical supervision. During these days blood samples for PK analysis will be collected as per the schedule mentioned in Table 1-3. In addition to PK samples, patients will be monitored for cardiac effects using 12-lead electrocardiograms (ECGs) (Table 1-2). NOX66 will be self-administered by the patients or administered by their care giver at home on all other dosing days as well as the evening doses of NOX66 on PK days (Cycle 1: Days 2, 6 and 14; Cycles 2 and 3: Day 1). The evening dose of Day 1 of Cycle 1 (in Part 1 only) will be administered at the clinical unit. Patients or care givers should always wear gloves when handling and/or during administration of NOX66. The use of a small amount of water-soluble lubricant is advised before rectal administration. Further administration and handling instructions are provided in the "Instructions for Administration of NOX66 Suppositories" document. Patients will also attend the study center for EBRT (8 Gy or 20/25 Gy given as 1 or 5 fractionated doses, respectively) on Days 2 to 11 of Cycle 1 depending on the number of fractions administered. From Cycle 2 onwards only NOX66 will be administered for 7 days followed by a 7-day rest period (as indicated above). Patients with mCRPC may also receive androgen deprivation therapy as maintenance therapy and patients with BC may receive background hormonal therapy during this study. No other anticancer therapy will be allowed during the study. Patients will have an End of Treatment (EOT) Visit within 7 to 10 days after the last dose of study drug. If a patient discontinues the study early (Early Discontinuation [ED]), the patient will have an ED Visit within 7 to 10 days after the last dose of study drug.

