Patients in both study parts will be followed up by phone for adverse events (AEs)/serious adverse events (SAEs) for 30 days after the last dose of study drug or until resolution or stabilization of ongoing AEs/SAEs deemed at least possibly related to the study drug, whichever is longer. All patients (including patients who discontinued the study early for reasons other than disease progression) will be followed up approximately every 12 weeks (± 2 weeks) after completion of the treatment period for disease progression up to 12 months, and for safety until death or the patient is lost to follow-up. Patients who discontinued the study early for reasons

other than disease progression will attend the clinical unit for the follow-up visits. Patients will receive the study drug until disease progression, unacceptable toxicity, withdrawal of consent, initiation of new anticancer therapy, withdrawal of the patient by the Investigator or termination of the study by the Sponsor. Patients who discontinued from the study for reasons other than progression will have tumor imaging and disease response assessments performed for up to 12 months after the last dose of study drug until disease progression, withdrawal of consent, initiation of new anticancer therapy, the patient is lost to follow-up or death, whichever comes first.

The study schemes are provided in Figure 1-1 (Part 1) and Figure 1-2 (Part 2), and the Schedule of Activities is provided in Table 1-1 (Parts 1 and 2).

Part 1 (Dose Escalation)

Approximately 30 patients with any solid tumor who require low-dose EBRT will be enrolled sequentially to the four planned NOX66 dose groups (Dose Cohort 1: 800 mg [3 to 6 patients]; Dose Cohort 2: 1200 mg; Dose Cohort 3: 1600 mg; Dose Cohort 4: 2400 mg [3 to 8 patients in each of Dose Cohorts 2 to 4]; total daily dose administered twice a day [BID]). At least 2 patients enrolled in Dose Cohorts 2 to 4 must have mCRPC.

The proposed dose regimen for Part 1 is given in the table below. No intra-subject dose escalation is allowed.

		Dose Cohort									
	1	2	3	4							
Total daily dose	800 mg	1200 mg	1600 mg	2400 mg							
Dosing regimen	400 mg BID	600 mg BID	800 mg BID	1200 mg BID							
Number of suppositories per day	$2 \times 400 \text{ mg}$	2 × 600 mg	$4 \times 400 \text{ mg}$	4 × 600 mg							

Proposed Doses for NOX66 (Part 1)

BID = twice daily

All patients will be closely monitored for any dose-limiting toxicities (DLTs) up to Day 21 of Cycle 1.

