4.4 End of Study Definition

Once a patient completes or discontinues study drug, he/she will be followed up every 12 weeks $(\pm 2 \text{ weeks})$ after the last dose of study drug for disease progression up to 12 months, and for safety until death or the patient is lost to follow-up.

For the entire study, study completion is defined as the last visit of the last patient for any protocol related activity (last patient, last visit), including telephone contact. For individual patients, study completion is defined as the time of the patient's last data collection.

The study will finish when the last patient enrolled in Part 2 completed 6 months of treatment; all patients receiving study drug at that time will be switched to the NOX66 compassionate access program. Those patients on the compassionate access program will continue to receive NOX66 treatment until disease progression or unacceptable toxicity. These patients will be followed until death, or the patient is lost to follow-up.

5 Study Population

The study population will consist of patients with mCRPC, BC, NSCLC or other solid tumors who have failed at least one line of prior treatment and for whom, according to the Investigator, are eligible for low-dose EBRT for at least one symptomatic or minimally symptomatic lesion (for the prevention of symptoms).

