7.1 Discontinuation of Study Drug

7.1.1 Safety Stopping Criteria:

It may be necessary for a patient to permanently discontinue (definitive discontinuation) study drug. If study drug is definitively discontinued, the patient will remain in the study to be evaluated for clinical observation and safety monitoring. See the SoA (Table 1-1 [Parts 1 and 2]) for data to be collected at the time of discontinuation of study drug and follow-up and for any further evaluations that need to be completed.

Patients may be discontinued from study drug in the following situations:

- Patient decision. The patient free to discontinue study drug at any time, without prejudice to further treatment.
- Any AE that in the opinion of the Investigator or Sponsor contraindicates dosing or meets the criteria for discontinuation.
- Recurrence of the same Grade 3 AE, even if recurrence is at a lower dose of study drug, with the exemption of localized skin reactions associated with drug administration which responds to topical corticosteroids.
- Unacceptable toxicity.
- Severe noncompliance with the protocol.
- Disease progression or unacceptable toxicity.
- Patient started alternative anticancer therapy including another investigational agent.
- Patient is lost to follow-up.

For patients with mCRPC, study drug will not be stopped due to rises in PSA alone. The Prostate Cancer Working Group 3 (PCWG-3) emphasized the importance of keeping patients on the study until radiographic or symptomatic progression, which better reflects the clinical course.

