7.2 Participant Discontinuation/Withdrawal from the Study

A patient may withdraw from the study at any time at his/her own request or may be withdrawn at any time at the discretion of the Investigator for safety, behavioral or administrative reasons. The patient will be definitively discontinued from both the study drug and from the study at that time.

The primary reason for a patient withdrawing prematurely should be recorded in the patient's source records and on the eCRF. In the absence of a medical contraindication or significant protocol violation, every effort will be made by the Investigator to keep the patient in the study. Patients who discontinue study drug because of an AE but agree to participate with any follow-up assessments will undergo the EOT/ED Visit and will be requested to return for the Follow-up Visits. The Investigator must contact the Medical Monitor promptly when deciding if a patient should be withdrawn or if the patient elects to stop the study.

Patients withdrawn from this study cannot re-enroll. Patients who discontinue for a non-safety related reason may be replaced if the patient is withdrawn during Cycle 1 in Part 1. Withdrawal of consent must be ascertained and documented by the Principal Investigator who must consult with the Medical Monitor and document the withdrawal of consent in the eCRF and in the medical records. Patients will be asked about the reason(s) for withdrawal and the presence of any AEs. Should the patient agree to be followed for safety information, this should be documented in the medical records.

Patients experiencing adverse reactions should be followed until the AE has resolved, stabilized or is no longer deemed clinically significant, as judged by the Investigator. Appropriate supportive and/or definitive therapy will be administered as required.

If the patient withdraws consent for disclosure of future information, the Sponsor may retain and continue to use any data collected before such a withdrawal of consent.

If a patient withdraws from the study, he or she may request destruction of any samples taken and not tested and the Investigator must document this in the site study records.

At the time of discontinuing from the study, if possible, an early discontinuation visit should be conducted, as shown in the SoA. Refer to the SoA (Table 1-1 [Parts 1 and 2]) for data to be collected at the time of study discontinuation and follow-up and for any further evaluations that need to be completed.

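### Section 8.1.8 lists early discontinuation, without restriction, as a PFS endpoint and then censors patients alive and progression-free; if it counts as an event, Kaplan-Meier PFS can only be lowered

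*Combined protocol and SAP*

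**What the plan says.** Section 8.1.8 ends PFS at the "date of disease progression is objectively documented, including tumor progression, early discontinuation or death prior to data cut-off". It continues: "Patients alive and progression-free at the time of data cut-off will be censored at the date last known alive". Assessment is every 8 weeks to Week 26 and every 12 weeks "thereafter until disease progression according to RECIST v1.1 criteria". The censoring date is the one that Section 8.1.9 uses for overall survival.

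Related text elsewhere in the protocol:

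- **Meaning of the term.** The Synopsis uses Early Discontinuation for leaving the study. Section 7.1.1 says that after definitive discontinuation of drug "the patient will remain in the study to be evaluated for clinical observation and safety monitoring". Section 7.2 uses the same visit label for stopping drug: "Patients who discontinue study drug because of an AE but agree to participate with any follow-up assessments will undergo the EOT/ED Visit".
- **Imaging after discontinuation.** Synopsis: "Patients who discontinued from the study for reasons other than progression will have tumor imaging and disease response assessments performed". The limit is 12 months from the final dose. Section 8.1.3 sets these scans every 12 weeks and ends them at progression, withdrawal of consent, new anticancer therapy, loss to follow-up or death. Section 4.4 follows patients "for disease progression up to 12 months, and for safety until death or the patient is lost to follow-up".
- **Progression criteria.** Section 8.1.3 names RECIST v1.1 and PCWG-3; Section 8.1.8 names RECIST v1.1 only.
- **PSA PFS.** Section 8.1.1 counts PSA progression or death and nothing else.
- **Analysis.** Section 9.4.7.2 gives Kaplan-Meier medians with 95% CIs and the 25th and 75th percentiles, by dose cohort or arm. Section 9.1 says that all analyses are descriptive. Section 9.4 leaves further detail to an SAP finalized before database lock; the supplied text contains no separate PFS rules.

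**The concern.** PFS should measure tumor control and survival. Patients may stop for reasons that are neither: Section 7.1.1 lists patient decision, adverse events, noncompliance and loss to follow-up. If such exits count as PFS events, the curve mixes tolerability and patient choice with progression. If they do not, the first sentence of the definition is wrong as it stands. Two programmers working from the protocol alone could produce different medians. In Part 1 cohorts of 3 to 8 patients, one reclassified patient is 12.5% to 33% of the cohort.

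The censoring date is a linked point. Vital status can be known long after imaging has stopped, so censoring at the date last known alive can credit a patient with progression-free time that nobody observed.

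**Working it through.** **1. Who is affected**

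| Patient discontinues | If discontinuation is an event | If it is not |
|---|---|---|
| because of documented progression | event at progression | same |
| without progression, then progresses or dies before cut-off | event at discontinuation | event later; only the date differs |
| without progression, alive and progression-free at cut-off | event | censored |

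Only the third row is contradictory. The contradiction goes if progression-free means free of any event just listed, but then discontinuation is an event.

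**2. Direction.** Let T be time to progression or death and D time to discontinuation without progression. Since min(T, D) ≤ T, counting D as an event can only lower the curve.

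**3. Size.** The documents state no PFS median or discontinuation rate, so there is no figure to reproduce.

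From the protocol: scans at weeks 8, 16 and 24, then every 12 weeks; 40 patients in Arm 1. Assumed: true median 6 months, so λ = ln 2/6 = 0.1155 per month; independent exponential times; share f discontinuing before progression, so δ = λf/(1−f).

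*Continuous detection.* Median = ln 2/(λ+δ) = 6(1−f), which gives 5.7, 5.1, 4.5 and 3.6 months for f = 5, 15, 25 and 40%, against 6.0.

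*Scan calendar.* Weeks 8, 16, 24 and 36 are 1.85, 3.69, 5.54 and 8.31 months. Documented PFS just after each scan is 2^(−t/6) = 0.808, 0.653, 0.527 and 0.383. It first falls below 0.5 at week 36, so the documented median is 8.3 months. With discontinuation as an event, multiply by exp(−δt):

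- f = 15%: δ = 0.0204. At week 24, 0.527 × 0.893 = 0.471; just before that scan, 0.653 × 0.893 = 0.583. Median 5.5.
- f = 25%: δ = 0.0385. At week 24, 0.527 × 0.808 = 0.426; just before, about 0.53. Median 5.5.
- f = 40%: δ = 0.0770. At week 16, 0.653 × 0.753 = 0.491; just before, 0.808 × 0.753 = 0.608. Median 3.7.
- f = 5%: δ = 0.00608. At week 24, 0.527 × 0.967 = 0.510, still above 0.5. Simulation, which adds deaths between scans, puts the crossing at about 7.3. This is the least stable value: without those deaths the curve is still at about 0.501 just before week 36.

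*Second parameterization.* If 20% discontinue by 6 months, 6-month PFS is 0.527 × 0.80 = 42.2%. A simulation on the scan grid also gave 42.2%, against 53.0% with progression or death only and imaging continued.

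**4. Censoring date.** These are simulations with assumed cut-off at 6 to 18 months and median survival of 9 months after progression. Early discontinuation is deleted as an event.

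- *Date last known alive kept.* There is no bias if discontinuers are scanned as planned. If none are scanned, the calendar median stays at 8.3, but the 75th percentile rises from 13.8 to 14.7 (f = 15%) or 16.6 (f = 25%). In a harsher model, where no later event of any kind is captured, the median moved to 11.1 in the case of 30% discontinuing by 6 months.
- *Last tumor assessment used instead.* The median is 8.3 except in three heavy cases: 8.0 (f = 25%, none scanned), 8.1 (f = 40%, half scanned) and 7.1 (f = 40%, none scanned). In those cases the 75th percentile is about 11.0 to 12.2 against 13.8.

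**The case against.** The sentence in 8.1.8 is ungrammatical. Its head is objectively documented progression, so early discontinuation may be a garbled reference to stopping because of progression. That stands. A reader might infer that the plan certainly treats every early discontinuer as progressed and that PFS will be biased; the documents do not support that. They support an unclear definition, with a downward bias on one reading.

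A reader might also infer that the two sentences collide for all discontinuers. They do so only for those alive and progression-free at cut-off.

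Continued imaging is not proof of intent either. The same scans serve disease control, response rate and duration of response, and PSA PFS is a different endpoint. Both suggest that discontinuation was not meant as an event, but no more.

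The SAP may yet set a rule, and its PFS rules cannot be seen here. But the protocol sentence would remain, and the SAP would have to depart from one reading of it.

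Finally, the upward bias from last-known-alive censoring is easily overstated. With continuous detection the median can read 8.0 against 6.0 (f = 40%, none scanned). On the protocol's own calendar the main runs show movement in the 75th percentile, not the median.

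**Conclusion.** The point holds as a definition that must be repaired. Early discontinuation is listed without restriction, the next sentence does not fit it, and nothing in Sections 9.4 or 9.4.7.2 settles the matter. The one reading that removes the contradiction makes discontinuation an event and lowers Kaplan-Meier PFS.

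The direction is certain on that reading; the size is not derivable from the documents. Every figure above rests on an assumed median, independent exponential times and assumed discontinuation shares. The 40% share is plausible only if the term covers stopping drug as well as leaving the study. With 40 patients and continuous detection, the typical 95% CI as written is 2.7 to 6.6 months at f = 25%, which still contains the true 6.0; at f = 40% it is 2.2 to 5.3, which does not.

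PFS is secondary and descriptive. No hypothesis test, primary endpoint or dose decision depends on it. It should be fixed, but it does not threaten the trial's main conclusions.

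**What to change.** In Section 8.1.8, carried into 9.4.7.2 and the SAP:

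- Define the PFS event as first objectively documented progression (RECIST v1.1, plus PCWG-3 for bone in mCRPC, in line with 8.1.3) or death from any cause.
- Delete early discontinuation. If it was never meant as an event, this only clarifies.
- Censor patients without an event at the last evaluable tumor assessment before any new anticancer therapy, instead of at the date last known alive. Make this change in the same edit.

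A sensitivity analysis counting clinical progression without a new scan as an event is optional; the case for it rests on assumed rates.

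The change needs wording and programming only, with no new visits or scans. It costs precision. With 40 patients, 25% discontinuing, up to half of them unscanned and continuous detection, expect about 28 to 29 events instead of 33 and a typical 95% CI for the median of about 3.5 to 9.2 months instead of 2.7 to 6.6. Censoring at the last assessment also has a modest downward bias if many discontinuers go unscanned, so the report should state how many were imaged after discontinuation.

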- * The procedures detailed at Cycle 5 Day 1 will be performed for all subsequent on-site visits (unless otherwise specified). Patients will continue NOX66 administration in each cycle from Day 1 until Day 7 followed by a 7-day rest period (Days 8 to 14).

It is important that PK sampling occurs as close as possible to the scheduled time. In order to achieve this, other assessments scheduled at the same time may be initiated prior to the timepoint. The order of assessments (as applicable to study visit) that should occur before dosing is: 1) PRO questionnaires, 2) vital signs, 3) ECG, 4) PK sampling, 5) dose administration. Blood sampling for safety laboratory assessments will be done prior to dosing. The order of assessments (as applicable to the study visit) that should occur after dosing is: 1) vital signs, 2) ECG, 3) PK sampling. All other procedures can be completed (as applicable to study visit) after the PK sample has been collected. It is critical that the patients record the time of dose in their Patient Study Drug Administration Diary for the PK assessment and the site record the time of blood sampling.

- ^{a.} End of Treatment Visit (EOT) occurs 7 to 10 days after the last dose of study drug. Assessments completed within 7 days prior to the last dose of study drug do not need to be repeated. If a patient discontinues from the study early (Early Discontinuation [ED]), they will have an ED Visit within 7 to 10 days after the last dose of study drug.
- ^{b.} For patients who permanently discontinue study drug for any reason other than confirmed disease progression, tumor imaging and disease response assessments will continue to be performed every 12 weeks (± 7 days) for up to 12 months after the last dose of the study drug until disease progression, withdrawal of consent, initiation of new anticancer therapy, the patient is lost to follow-up or death, whichever comes first.
 - If a patient meets disease progression during the follow-up period according to RECIST v1.1 criteria, a tumor imaging and disease response assessment is not required.
 - If a patient permanently meets clinical disease progression during the follow-up period, a tumor imaging and disease response assessment does not need to be repeated if completed ≤ 28 days after the date of clinical disease progression.
 - Patients who have met disease progression will be contacted every 3 months for survival follow-up.

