8.1.3 Tumor Imaging Assessment

In this study, the preferred assessment of soft tissue lesions is CT or MRI scans using RECIST v1.1 criteria and the preferred assessment method for bone lesions is bone scan using PCWG-3.

Tumor imaging using RECIST v1.1 and PCWG-3 criteria will be performed during within 28 days prior to enrollment, every 8 weeks (\pm 7 days) from the first study dose administration up to Week 26, and every 12 weeks (\pm 7 days) thereafter until disease progression (as defined by RECIST v1.1 and PCWG-3 criteria), withdrawal of consent, initiation of new anticancer therapy or death. Tumor imaging should ideally be performed during the rest period before the start of the next treatment cycle.

- If a patient permanently discontinues the study drug due to disease progression according to RECIST v1.1 criteria, a tumor imaging and disease response assessment is not required.
- If a patient permanently discontinues the study drug due to clinical disease progression, a tumor imaging and disease response assessment does not need to be repeated if completed ≤ 28 days after the last dose of study drug.

For patients who permanently discontinue study drug for any reason other than confirmed disease progression, tumor imaging and disease response assessments will continue to be

performed every 12 weeks (\pm 7 days) for up to 12 months after the last dose of the study drug until disease progression, withdrawal of consent, initiation of new anticancer therapy, the patient is lost to follow-up or death, whichever comes first.

- If a patient meets disease progression during the follow-up period according to RECIST v1.1 criteria, a tumor imaging and disease response assessment is not required.
- If a patient meets clinical disease progression during the follow-up period, a tumor imaging and disease response assessment does not need to be repeated if completed ≤ 28 days after the date of clinical disease progression.

For patients who permanently discontinue the study drug or the follow-up period due to withdrawal of consent, the Investigator is to obtain tumor imaging and conduct a disease assessment at the time of the ED Visit or final Follow-up Visit if the patient agrees. A tumor imaging and disease response assessment does not need to be repeated if completed ≤ 28 days of the date of withdrawal of consent.

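### PFS is censored at the date last known alive rather than at the last tumour assessment, so a patient whose imaging ends before contact does is credited with unassessed time as progression-free

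*Combined protocol and SAP*

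**What the plan says.** Section 8.1.8 measures PFS from first dose to objectively documented progression, and describes its events as "including tumor progression, early discontinuation or death prior to data cut-off". It then gives the censoring rule: "Patients alive and progression-free at the time of data cut-off will be censored at the date last known alive". The assessments behind PFS are RECIST v1.1 scans every 8 weeks to Week 26 and every 12 weeks after that. Section 8.1.9 censors overall survival at the same date.

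Section 8.1.3 sets when imaging stops. Apart from progression itself, the stopping points are "withdrawal of consent, initiation of new anticancer therapy or death". Patients who stop drug for a reason other than confirmed progression are scanned every 12 weeks "for up to 12 months after the last dose of the study drug", ending earlier at progression, "withdrawal of consent, initiation of new anticancer therapy, the patient is lost to follow-up or death, whichever comes first".

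Contact runs longer. The Synopsis and Sections 4.1 and 4.4 follow patients "for disease progression up to 12 months, and for safety until death or the patient is lost to follow-up". Of patients moved to compassionate access, Section 4.4 says: "These patients will be followed until death, or the patient is lost to follow-up". No imaging schedule is given for that program.

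Section 9.4.7.2 reports PFS as Kaplan-Meier medians, quartiles and range by dose cohort or arm. Section 9.4 leaves further detail to the SAP; the documents contain no other PFS censoring text.

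**The concern.** A phone call can establish that a patient is alive. It cannot establish that the patient is free of RECIST progression. Where scans have ended and contact has not, the rule keeps the patient in the risk set without any means of recording a progression. Death is then the only event that can still be observed.

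Three groups can be affected: patients who start new anticancer therapy before progression, patients more than 12 months past their last dose without progression, and patients contacted after the switch to compassionate access.

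PFS is a secondary, descriptive endpoint. No test or sample size depends on it, but no control arm offsets a bias either. Part 1 cohorts hold 3 to 8 patients, so one long unassessed interval can alter the reported upper quartile or range.

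**Working it through.** The plan gives no PFS rate, event count or power, so there is no stated figure to reproduce. The check has two parts.

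**1. The gap for one patient.** Gap = censoring date minus end of imaging.
- Illustration: new therapy at month 3 without progression, alive at a cut-off at month 18. Gap = 18 - 3 = 15 months counted as progression-free with no scan due.
- Patient still on drug and scanned on schedule: the gap is at most one scan interval, 12 x 7 / 30.4375 = 2.8 months.

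**2. The effect on a cohort.** Large-sample Kaplan-Meier simulation, 100,000 patients per scenario.

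From Section 8.1.3: scans at weeks 8, 16 and 24, then every 12 weeks; imaging ends at new therapy or 12 months after stopping drug.

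Assumed, because the documents do not give them:
- exponential times, with median time to progression 4, 6 or 9 months;
- 0, 2% or 5% per month stopping drug without progression, of whom 50% or 100% start new therapy at once;
- median survival after progression 10 months, and median time to death without progression 40 months;
- 18 months of accrual, cut-off 6 months after the last patient enters, contact kept to cut-off.

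True PFS for the 6-month case:
- Hazard = ln2/6 + ln2/40 = 0.1155 + 0.0173 = 0.1329 per month.
- Median = ln2/0.1329 = 5.2 months.
- 12-month PFS = exp(-12 x 0.1329) = 20%.

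Results for that case, as median in months and 12-month PFS:

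| Stop per month; share to new therapy | Last known alive, discontinuation not an event | Last scan | Last known alive, discontinuation an event |
|---|---|---|---|
| 0 | 5.5; 23% | 5.5; 22% | 5.5; 23% |
| 2%; 50% | 5.5; 25% | 5.5; 22% | 5.5; 18% |
| 2%; 100% | 6.0; 26% | 5.5; 22% | 5.5; 18% |
| 5%; 50% | 6.2; 27% | 5.5; 22% | 4.0; 12% |
| 5%; 100% | 7.7; 32% | 5.5; 22% | 3.9; 12% |

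The last-scan column sits slightly above the truth (5.5 against 5.2 months) because progression is dated at the scan that detects it.

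**Discontinuation not an event.** Across all three progression medians, with 2-5% per month stopping:
- 12-month PFS rises over the last-scan value by between 36 - 34 = 2 points (9-month case) and 32 - 22 = 10 points (6-month case).
- The median rises by between 0 and 7.7 - 5.5 = 2.2 months.
- With nobody stopping early, the difference is about 1 point and the median does not move.

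**Discontinuation an event.** With 2-5% per month stopping:
- 12-month PFS is 12-18% against a true 20% (6-month case) and 19-27% against 32% (9-month case).
- Patients still censored have a median gap of about 1.4 months and a maximum of 2.8.

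Two limits apply. The last-scan column also censors deaths that occur after imaging has ended; a rerun that kept those deaths as events gave essentially the same ranges. Contact under compassionate access was not simulated.

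**The case against.** The strongest objection is the event list. If early discontinuation is a PFS event, patients who stop drug for new therapy or any other reason have their event then and never reach the censoring rule. A reader might infer that PFS is overstated overall, whichever way Section 8.1.8 is read. The documents do not support that: under the literal event list the simulated 12-month PFS falls below the truth. What stands against the literal list is the rest of the protocol. Section 7.1.1 keeps a patient in the study after drug is definitively stopped, and Section 8.1.3 keeps scanning such patients until progression, which would add nothing to PFS if stopping were already the event. The text is ambiguous and has to be settled.

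A reader might also describe the affected patients as being in survival follow-up. Table 1-1 footnote b says: "Patients who have met disease progression will be contacted every 3 months for survival follow-up", and footnote y limits the survival-status visit to the same group. Patients without progression are in safety follow-up.

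Clinical progression without RECIST progression might look like a further affected group. Section 8.1.3 waives a scan only where a recent one exists, and continues imaging unless progression is confirmed. Such patients may also not count as progression-free. How to classify them is mainly a separate question.

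The compassionate-access gap depends on a data cut-off that is not dated. The switch coincides with the end of the study, and nothing says whether later contacts enter the PFS analysis.

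Finally, sampling error is large. Assuming 35 events among the 40 Arm 1 patients and exponential times, the 95% interval for a 6-month median is 6 x exp(±1.96/√35), or about 4.3 to 8.4 months. That limits the practical weight of a small shift. It does not justify a rule with a known direction of bias when scan dates are already collected.

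**Conclusion.** The censoring date is wrong for an endpoint assessed by imaging. For each patient censored after scans have ended, the error favours longer PFS.

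The net effect on reported PFS is conditional. If early discontinuation is not an event, the overstatement is about 2-10 percentage points at 12 months and 0 to about 2 months in the median. If it is an event, net PFS can be understated, and the censoring gap shrinks to at most about one scan interval, apart from any compassionate-access contact.

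These sizes rest on the assumed rates above and show direction and range only. A statement that the plan overstates PFS in all cases would go further than the text allows. The point should be corrected, but its weight is moderate because PFS is secondary and descriptive.

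**What to change.** In Section 8.1.8 and the SAP:

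- Censor patients without documented progression or death at their last evaluable tumour assessment, taken on or before the start of any new anticancer therapy. With no post-baseline assessment, censor at first dose.
- Keep the date last known alive for overall survival only.
- State whether early discontinuation is a PFS event, and reconcile the event list with the imaging that continues after drug is stopped. Changing the censoring sentence alone would leave the two in conflict.
- Define the data cut-off relative to the compassionate-access switch.

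Clinical-only progression, and deaths after new therapy or missed scans, can be handled in sensitivity analyses. Censoring such deaths is a choice of estimand and can itself be informative, so it need not be part of the primary rule.

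The cost is protocol and SAP wording. No new data are needed. The downside is that reported PFS may be slightly shorter.
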